Research objectives	
Primary Objective: To evaluate the effectiveness of reactive case detection (RACD) using HS-RDTs, targeting both village and forest working populations, compared to control for reducing the health center catchment-level incidence and prevalence of P. falciparum and P. vivax within two provinces in Lao PDR.
 
Secondary Objectives:
 
 1. To determine the operational feasibility, cost-effectiveness, and acceptability of targeting high-risk populations with community-based reactive case detection strategies aimed at reducing P. falciparum and P. vivax transmission among village and forest working populations. 2. To determine the operational feasibility and safety of conducting G6PD testing and PQ administration and follow-up at the community level. 3. To determine factors associated with G6PD testing after referral to district or provincial-level facilities for persons with P. vivax positive RDT results, and subsequent adherence to Primaquine treatment. 4. To assess malaria vector species composition and bionomics in both village and forest settings
Study site and target populations	Total population of approximately 120,000 in 32 health center catchment areas of two Provinces in Lao PDR (Champasak and Saravan Province)
Study design	A cluster randomized controlled trial design will be used to evaluate the enhanced RACD intervention against standard of care
Primary outcome measures for assessing impact	
 1. Cumulative incidence over the study period at the health facility level 2. Prevalence of infection (P. falciparum and/or P. vivax) using qPCR 3. HS-RDT and RDT test positivity rate for RACD
Data collection and sampling period	18 months from start date (June 2019 – November 2020)

Sample size	32 health center catchment areas in Lao PDR

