2.5. Study overview

To test this hypothesis, this study will employ a cluster randomized controlled trial design with two comparison arms:

1. **Control:** standard of care - passive case management provided through community-based VMWs and existing health facilities; includes village-based RACD with conventional RDTs conducted by district surveillance teams.
2. **Enhanced community-based RACD:** RACD conducted by community-based VMWs using both HS-RDTs and conventional RDTs within villages and among forest workers.

The primary outcome measures to assess effectiveness include *P. falciparum* and *P. vivax* confirmed case incidence over the study period; PCR-based *P. falciparum* and *P. vivax* prevalence at endline; and HS-RDT test positivity rate in village and forest worker RACD. Secondary outcomes measures will examine the operational feasibility, safety, and acceptability of VMW-led reactive approaches and G6PD testing, referral to district or provincial-level facilities, safety and treatment adherence for *P. vivax* cases. The trial will be implemented between June 2019 and December 2020 in Lao PDR. The primary evaluation will be conducted following an end-line cross-sectional survey in November/December 2020.

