3.4.2.3. Primary outcome measures

1. Confirmed *P. falciparum* and *P. vivax* malaria parasite incidence: defined as the number of OPD malaria confirmed and suspected cases per person per year for each HCCA, as ascertained from the health facility registers, utilizing administrative catchment population size estimates for the exposure denominator.
2. PCR-based *P. falciparum* and *P. vivax* parasite prevalence in sampled HCCAs: defined as the proportion of individuals ≥ 18 months old with *P. falciparum* or *P. vivax* infection (detected by PCR) out of all individuals ≥ 18 months tested within the endline survey (2020).
3. HS-RDT/RDT -based test positivity rate in village and forest-based reactive case detection: defined as the proportion of all individuals tested by HS-RDT/RDT in response to an index cases, with a positive HS-RDT/RDT, among the population older than 18 months.

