3.4.2.6. Data management and analysis

Data will be collected via ODK-based tablet application with internal range checks or paper-based with subsequent double-entry, and will be stored in Microsoft Excel or Access. The number of malaria cases, based on RDT and PCR results, will be mapped by village or sub-village and compared between surveys.

Primary outcomes

Outcome 1: Community-level confirmed *P. falciparum* and *P. vivax* malaria parasite incidence

Data pertaining to this outcome will be analyzed on an intention-to-treat basis at the level of health facility catchment area (randomization unit). Cumulative counts of confirmed malaria cases from the health facility registers over the study period and the previous year will be analyzed in a Poisson or

negative binomial regression model with random intercepts at the health center catchment level and an offset for the estimated population size of the catchment area (from administrative data). The models will include a fixed effect for each study arm and a fixed effect for time period (pre- and post-intervention start). The interaction between these two terms will be the primary effect measure (also known as the difference-in-differences estimator). Pre/post-intervention will be determined as all time periods before the start date of the intervention in the areas considered as being pre-intervention and all time periods after (and including the start date of the intervention in the area considered as being post-treatment).

Outcome 2: Community-level PCR-based *P. falciparum* and *P. vivax* parasite prevalence in sampled villages

The effectiveness of the interventions will be assessed as *P. falciparum* and *P. vivax* prevalence via PCR at end-line (post only) using generalized linear mixed effects models with separate random intercepts to allow for clustering within health center catchments. The binomial distribution will be used to analyze prevalence outcomes (logistic regression). All main analyses will be analyzed as intention-to-treat, and all survey clusters will be analyzed within the intervention group assigned at randomization, regardless of adherence. The primary effect estimate will be evaluated using the fixed effects for RACD. Secondary analyses will include adjustment for age, sex, and other potential confounders, and a per-protocol analysis of the primary effect estimate.

Outcome 3: HS-RDT and RDT-based test positivity rate in village-based and forest-based samples

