The adverse event rate for RDT positive participants will be assessed using intervention data and health facility adverse event reporting forms. Study staff and VMWs will be trained on detection of adverse events for positive cases receiving treatment.

Outcome 5: Operational feasibility of G6PD referral, testing and non-adherence

The operational feasibility of G6PD referral, testing and non-adherence at the community and facility levels will be evaluated. For testing, interview data at baseline and endline will be collected from district health staff and community members, as well as focus group discussions with both groups at end-line. Risk factors for non-adherence to G6PD testing after referral will be determined through comparison of factors captured at enrollment for individuals who were tested at a facility versus those who were not.

Outcome 6: Assessment of *P. vivax* treatment adherence

The treatment adherence of *P. vivax* positive study participants will be assessed through physical evidence of adherence during VMW follow-up visits on day 3, 7 and 14 and comparison of relapse rates across study arms.

3.4.4. Assessment of the risk of malaria vector biting in forest and village settings

A baseline entomological investigation will be conducted along with the baseline qualitative activities in Aug/Sep 2019. The investigation will involve collection of vector occurrence and density data (by species), human landing catches (HLC) to assess vector biting behaviors (indoor vs outdoor and forest sites), and household structure type, and human behavioral observations. All collections will take place over a one-week period. HLC collections will occur in 4-5 sleeping structures each in the forest and village, with 2 HLC collectors by structure. At the end of each HLC collection hour, collectors will also record human behavior (sleeping (or awake) under net/sleeping without net/awake), both indoors and outdoors. Field collectors will be community volunteers that will have been properly informed about the sampling methods and their implications, and who have consented to participating by signing consent forms. Prior to the start of collections, volunteers will also need to be tested for malaria. Depending on national policy, they may also be required to take malaria prophylaxis. HLC data collection forms are found in the Appendix.

4 Ethical issues related to human subjects research

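### The primary before/after cut is tied to an intervention start date that control catchments do not have, and the offset omits time at risk, so the interaction is biased if cut dates differ between arms

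*Protocol*

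**What the plan says.** Protocol section 3.4.2.6 (Outcome 1) models "Cumulative counts of confirmed malaria cases from the health facility registers over the study period and the previous year" by Poisson or negative binomial regression, with a random intercept for each health center catchment and "an offset for the estimated population size of the catchment area". The fixed effects are arm and period, and their interaction is the primary effect measure.

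The same section sets the cut. The before period is "all time periods before the start date of the intervention in the areas considered as being pre-intervention"; the after period is everything later, "including the start date of the intervention in the area considered as being post-treatment".

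Section 3.4.2.3 expresses the outcome as cases "per person per year for each HCCA", but it too names only catchment population as the denominator.

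On timing, the protocol summary gives "18 months from start date (June 2019 – November 2020", and section 2.5 says "The trial will be implemented between June 2019 and December 2020 in Lao PDR". Control catchments receive standard of care (sections 2.5 and 3.4.2.2).

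**The concern.** The cut rule refers to an event that happens in only one arm. The 16 control catchments need a cut date before the interaction can be computed, and the protocol gives none. The analyst has to choose one, and the natural choice is the nominal trial start.

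If RACD catchments are then cut at their actual local start, the two arms have before and after windows of different lengths. With population as the only offset, the model reads fewer months as fewer cases. The difference goes into the interaction, which is the treatment effect. The target effect is a 50% reduction (section 3.4.2.4.1), so an artefact of 10% to 30% would change the trial's conclusion.

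**Working it through.** The plan gives no figure for the split itself, so there is none to reproduce. The check asks what ratio the interaction returns when there is no true effect.

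**Inputs.** From the protocol: a before window of 12 months (the previous year), an after window of 18 months (June 2019 to November 2020), and population as the only offset. Assumed: the mismatch k in months between the RACD cut and the control cut, and the seasonal pattern in step 3.

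**Formula.** Expected interaction = (RACD after / RACD before) ÷ (control after / control before), where each term is an expected count per head.

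**Step 1: one common date.** (18/12) ÷ (18/12) = 1.00. The unequal window lengths go into the period main effect. A 3-month delay in both arms gives (15/15) ÷ (15/15) = 1.00.

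**Step 2: RACD cut differs, control cut at June 2019, level incidence.** Control after/before = 18/12 = 1.5.

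| RACD cut | Before window kept at 12 months | Before window runs from June 2018 to the cut |
|---|---|---|
| 1 month early | (19/12)/1.5 = 1.06 | (19/11)/1.5 = 1.15 |
| 1 month late | (17/12)/1.5 = 0.94 | (17/13)/1.5 = 0.87 |
| 2 months late | (16/12)/1.5 = 0.89 | (16/14)/1.5 = 0.76 |
| 3 months late | (15/12)/1.5 = 0.83 | (15/15)/1.5 = 0.67 |

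A simulation with the protocol's planning values (16 + 16 catchments, population 4000, 2.5 per 1000 per year, coefficient of variation 0.6) reproduced these ratios. It used 400 runs per setting, a Poisson within-catchment contrast, and catchment rates that did not change over time. At a nominal two-sided 5% level, false-positive rates for delays of 1, 2 and 3 months were about 17%, 48% and 82% with the late months moved into the before period. With that period kept at 12 months they were about 7%, 13% and 21%. With a common date the rate was about 4%. With log(population × time) as the offset and no seasonality, the ratio returned to 0.99–1.01.

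**Step 3: does a person-time offset suffice alone?** Assume June–November incidence is three times December–May (3 units a month against 1).

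- Control: before 6×3 + 6×1 = 24; after 18 + 6 + 18 = 42.
- RACD 3 months late: after 42 − 9 = 33; before 24, or 24 + 9 = 33 if the late months move.
- Population-only offset: (33/24)/(42/24) = 0.79, or (33/33)/(42/24) = 0.57.
- Person-time offset: control (42/18)/(24/12) = 1.167. RACD (33/15)/(24/12) = 1.10, ratio 0.94; or (33/15)/(33/15) = 1.00, ratio 0.86.

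Person-time alone therefore leaves 0.86 to 0.94, because the arms still compare different mixes of months.

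**The case against.** The strongest reply is that the protocol plans one June 2019 start and nowhere describes a staggered launch. Section 3.4.2.6 itself first names common windows, the study period and the year before it. Under those the interaction is unbiased even without a time term. The cut sentence is also garbled: it says areas in one half and area in the other, with a misplaced parenthesis, and it could mean one programme-wide date. Its plural time periods could mean equal-length rows such as months, for which a population offset would largely suffice. Exact window dates and the form of an offset are often left to an SAP.

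Much of this stands, and it makes the harm conditional. It does not remove the point. The protocol itself states the cut rule, the offset and the effect measure. The words about the area, and the use of cumulative counts, favour the problematic reading. No reading supplies a control date unless one assumes a programme-wide start.

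Four stronger inferences are tempting but not supported:

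- **That any later or staggered start produces a false reduction.** The bias needs cut dates that differ between arms. A common delay gives none, and an early RACD cut gives a false increase. In the simulation the same 0–6 month stagger in both arms averaged 1.00, although false positives rose to about 11%.
- **That launch was in fact late.** Section 3.4.4 says "A baseline entomological investigation will be conducted along with the baseline qualitative activities in Aug/Sep 2019", but ties no launch date to that work. If it did imply a later launch, that would most naturally be programme-wide.
- **That the November and December 2020 end dates add to the bias.** An end date shared by both arms cannot create a difference between their starts, and December is largely explained by the endline survey.
- **That intention-to-treat is broken.** Catchments stay in their allocated arm; what is at issue is the time origin.

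**Conclusion.** The point holds in conditional form. As written, the primary contrast has no defined cut for half the catchments, and its offset does not match its own outcome definition. With one common date there is no bias. If RACD catchments are cut 2 to 3 months later than controls, the false ratio under no effect and level incidence is 0.83 to 0.89 with the before window held at 12 months, and 0.67 to 0.76 if it absorbs the late months. The worst of these is an apparent one-third reduction against a 50% target. The delay lengths and the 3:1 seasonality are assumptions; the documents give neither. What justifies the change is that a stated rule for the primary effect can be read in ways that give 1.00 or 0.67 on the same data.

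**What to change.** Replace the cut sentence in section 3.4.2.6 with one rule for all 32 catchments, along these lines: *For every catchment in both arms, whatever its local launch date, the before period is the 12 months ending the day before the common trial start date, and the after period is the 18 months from that date. The offset is log(population × years in the period).* State the calendar dates. Record local start dates and use them in a sensitivity analysis only, with a stated rule for assigning dates to control catchments.

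The common date is the essential part, since step 3 shows that a person-time offset alone does not remove the bias when cases are seasonal. The offset still belongs in the model, so that the period effect and the reported rates match the outcome definition.

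The cost is a change of wording. The current rule already needs cases that can be placed before or after a date, so no new kind of data is required. The downside is that catchments launching late contribute some unexposed months to the after period. That dilutes the effect slightly towards no difference, which an analysis by allocation accepts.

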3.3. Interventions

Each intervention cluster (i.e., health facility catchment area) will be randomly assigned to either the RACD intervention or control arm (in a 1:1 ratio) before the study begins. The randomization process is described in more detail in section 3.4.2.2 below. Interventions (RACD) will be conducted by VMWs and/or community volunteers in response to an index case (presenting to VMW, malaria post, health facility, or other testing facilities) occurring anywhere within a selected intervention health facility catchment area. At presentation, all index cases will initially be asked about recent forest exposure. The intervention response for cases with no history of forest exposure in the past two months will be conducted only at the village level, while the response for cases with history of recent forest exposure will include both village and forest-worker populations. Forest-worker RACD will be conducted at recent work sites if accessible and located within the health facility catchment and/or amongst peer forest-goers referred by the index case. VMWs in intervention villages will maintain a register of forest workers and locations to assist them with tracking. In Lao PDR, health center staff will assist with RACD during the first six months of the study only, after which point VMWs will operate independently.

Index case capture

Interventions will be initiated after an individual from a cluster assigned to an intervention is diagnosed with malaria and notified to the study team. Suspected malaria cases attending local health services (hospital, health center, health post, or VMW) will be tested with an RDT or microscopy according to routine practice. All cases parasitologically confirmed by RDT will be treated according to national guidelines and asked for informed consent to participate in the study. If the patient gives informed consent, the VMW or health staff will promptly notify the study team using mobile phone. A short screening questionnaire will be administered to determine location of residence and recent forest or other travel. Additionally, finger prick blood will be collected on DBS from the index case for subsequent analyses.

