3.4.2.2. Randomization

A total of 32 health center catchment areas (HCCAs) in Laos will be selected for inclusion based upon incidence per 1000 population between October 2017 and September 2018. HCCAs with higher incidence will be prioritized to improve power; where possible, directly neighboring HCCAs will not both be included to reduce contamination. Restricted randomization of the HCCAs into either RACD or control arms will be conducted, whereby sets of randomizations (with 16 HCCAs in each arm) will be generated that achieve balance across arms on incidence per 1,000 over the prior year, population size, and amount of forest cover. From these sets of potential randomizations, a single randomization will be randomly selected to assign 16 HCCAs each to the RACD or control group. Restricted randomization in this way will ensure balance across intervention and control groups on potential confounding factors. The 'sample' command in Stata v14 (StataCorp, College Station, TX) will be used to implement randomization.

Table 5. Study arms

Study arm	Description	Lao PDR
RACD	Reactive case detection led by VMWs in response to cases in study area HCCA, with follow up testing with HS-RDTs/RDTs in both villages and forest workers; referrals for qualitative G6PD testing for P. vivax cases and 14-day PQ for G6PD non-deficient	16
Control	Standard of care including case management through health facilities and malaria posts/VMWs; village-based RACD conducted by district staff in some areas	16

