3.4.2.4.2. Population-level *P. falciparum* and *P. vivax* malaria parasite prevalence

Assuming 16 health catchment areas per arm, a baseline control prevalence by qPCR (all species) of 2.5%, and a coefficient of variation of 0.5, a minimum of 400 individuals per catchment area will be required in order to detect a 50% reduction in prevalence at endline. Assuming a 10% refusal rate, a total of 14,080 individuals will be required across both arms at the end-line survey. Assuming 4 individuals per household, this will result in a total of 3,520 households sampled, or 110 per health facility catchment area.

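### The primary endline prevalence analysis (Outcome 2) omits the three covariates used to restrict the randomisation; if they predict prevalence, its test is conservative and gives up a few points of power.

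*Protocol*

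**What the plan says.** Section 3.4.2.2 (Randomization) generates candidate allocations of 16 catchments per arm that achieve "balance across arms on incidence per 1,000 over the prior year, population size, and amount of forest cover", then draws one at random. It describes these variables as possible confounders.

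Section 3.4.2.6, Outcome 2, analyses PCR prevalence at endline only, in a logistic mixed model with a random intercept for catchment. It states: "The primary effect estimate will be evaluated using the fixed effects for RACD". No covariate is named for this model. Adjustment appears only afterwards: "Secondary analyses will include adjustment for age, sex, and other potential confounders". The section does not say which reference distribution or small-sample method the test will use.

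Outcome 1 in the same section differs. Its model includes the previous year's case counts and takes the arm-by-period interaction as the effect, so it carries baseline incidence. The primary Outcome 2 model carries no baseline information.

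**The concern.** Restricting allocation on a prognostic variable removes most of that variable's contribution to the difference between arms. A model without the variable still counts its contribution as random between-catchment variation. The standard error is then larger than the real variability of the estimate, the test rejects too rarely under the null, and the confidence interval is too wide. The balance does make the estimate more precise, but the reported standard error does not show it.

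Outcome 2 is one of three primary outcomes, and its formula power is only a little above 80% (see the working). Section 5.2 itself warns that falling malaria could reduce power, so a few points matter.

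**Working it through.** **Inputs from the protocol.** Section 3.4.2.4.2: "Assuming 16 health catchment areas per arm, a baseline control prevalence by qPCR (all species) of 2.5%, and a coefficient of variation of 0.5", and "a minimum of 400 individuals per catchment area will be required in order to detect a 50% reduction in prevalence at endline". Section 3.3: catchments are "randomly assigned to either the RACD intervention or control arm (in a 1:1 ratio"). Section 3.4.2.2: three restriction covariates.

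**Assumptions, because the protocol gives no figure.** Two-sided alpha 0.05; power 80%; share R² of between-catchment variance explained by the three covariates together, taken as 0, 0.3 and 0.6; balance tolerance of 0.5, 0.25 or 0.1 SD on each covariate.

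**Step 1: the plan's own figure.** Unmatched cluster formula, with m = 400, p0 = 0.025, p1 = 0.0125, k = 0.5:

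c = 1 + (1.96 + 0.84)² × [p0(1−p0)/m + p1(1−p1)/m + k²(p0² + p1²)] / (p0−p1)²

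The bracket is 0.0000609 + 0.0000309 + 0.0001953 = 0.0002871. Divided by 0.00015625 it gives 1.8375. Then c = 1 + 7.849 × 1.8375 = 15.42, so 16 per arm. The plan's size is reproduced at 80% power; 90% would need 21. Formula power with 16 per arm is 81.5% with the +1 term and 83.9% without it. The survey total also reproduces: 32 × 400 × 1.10 = 14,080.

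**Step 2: expected direction and size.** On the log scale, between-catchment variance is ln(1 + 0.5²) = 0.223. Sampling variance per catchment at 2.5% is about 0.975/(400 × 0.025) = 0.0975. The unadjusted model sees 0.223 + 0.0975 = 0.321. Under near-perfect balance, the variance that really drives the arm difference is (1 − R²) × 0.223 + 0.0975.

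- R² = 0.3: 0.254. Ratio of true to reported SE = √(0.254/0.321) = 0.890. Effective critical value 2.042/0.890 = 2.30; two-sided tail on t(30) about 2.9%.
- R² = 0.6: 0.187. Ratio 0.763. Effective critical value 2.68; tail about 1.2%.

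**Step 3: simulation.** 32 catchments of 400, k = 0.5, three independent, equally weighted covariates, allocation restricted on all three. The analysis is a cluster-level regression on log prevalence (0.5 added to each count), with 5,000 runs per cell. Unadjusted df = 32 − 2 = 30; adjusted df = 32 − 5 = 27.

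| Tolerance | R² | Type I, unadjusted t(30) | Type I, adjusted t(27) | Power, unadjusted | Power, adjusted |
|---|---|---|---|---|---|
| 0.5 SD | 0 | 4.7% | 5.2% | 84.5% | 82.4% |
| 0.5 SD | 0.3 | 3.8% | 5.0% | 86.3% | 88.7% |
| 0.5 SD | 0.6 | 2.9% | 4.9% | 86.5% | 93.3% |
| 0.25 SD | 0 | 5.2% | 4.9% | 85.5% | 84.8% |
| 0.25 SD | 0.3 | 2.9% | 4.6% | 85.4% | 89.0% |
| 0.25 SD | 0.6 | 1.8% | 4.9% | 87.0% | 94.0% |
| 0.1 SD | 0 | 5.3% | 5.2% | 84.7% | 84.4% |
| 0.1 SD | 0.3 | 2.7% | 4.9% | 86.0% | 89.6% |
| 0.1 SD | 0.6 | 1.4% | 5.1% | 88.4% | 94.8% |

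Monte Carlo SE is about 0.3 points for type I error (√(0.05 × 0.95/5000)) and 0.5 points for power. The 0.1 SD rows agree with step 2. At 0.25 SD, adjusting gains 3.6 points at R² 0.3 and 7.0 at R² 0.6, and costs 0.7 at R² 0. At 0.5 SD the figures are a gain of 2.4, a gain of 6.8 and a cost of 2.1.

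**Step 4: does adding covariates to the mixed model suffice?** Maximum-likelihood logistic mixed model, tolerance 0.25 SD, 3,000 null runs per cell:

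| R² | Unadjusted z | Unadjusted t(30) | Adjusted z | Adjusted t(27) |
|---|---|---|---|---|
| 0 | 6.6% | 5.8% | 8.3% | 7.0% |
| 0.3 | 4.7% | 3.5% | 8.2% | 6.7% |
| 0.6 | 2.3% | 1.8% | 7.6% | 6.6% |

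It does not. Adjustment inside this model with a simple z or t reference is liberal at every R².

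**The case against.** Four points can be made in defence of the plan.

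- **The covariates may predict little.** The restriction uses register incidence from October 2017 to September 2018, while the outcome is community PCR prevalence in November/December 2020. Section 2.1 reports steep recent falls in incidence, and section 5.2 allows for further large changes. This stands as a limit on size: at R² = 0 nothing is gained. Against it, district incidence in Table 1 runs from 2.23 to 18.25 per 1,000, and restricting on these variables makes sense only if they are expected to matter.
- **The error is in the safe direction.** Omitting the covariates lowers the false-positive rate, and the sample size still reproduces at 80% power. This stands, and it limits the severity.
- **Adjustment is already planned.** The open-ended secondary adjustment could include the three variables. This stands in part: the section still places adjustment outside the primary analysis.
- **Reference distributions belong in an analysis plan.** This stands in full. A reader might infer that the protocol commits to uncorrected mixed-model inference on 32 clusters and so has a known false-positive rate away from 5%. The text does not support that, because it names no z, t, bootstrap or permutation reference. Nor is the direction fixed: an uncorrected z test pushes the rate up, omitting the covariates pushes it down, and at R² = 0.3 the two nearly cancel (4.7%).

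**Conclusion.** The point holds as an improvement in efficiency and calibration. The protocol restricts allocation on three catchment-level variables and then fixes a primary Outcome 2 model without them.

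If they explain 30 to 60% of between-catchment variance, a t-referenced unadjusted test has a type I error of about 1.5 to 4%. It gives up roughly 3 to 7 points of power (2.4 at the loosest tolerance tried). If they explain nothing, adjustment costs about one point or less at tolerances of 0.25 SD or tighter, and about two at 0.5 SD.

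These sizes rest on assumed values of R², balance tolerance, alpha and power. A reader might go further and conclude that the primary test is invalid or the comparison underpowered. The figures do not support either: unadjusted simulated power was 84.5% or higher in every restricted cell.

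**What to change.** In section 3.4.2.6, define the primary Outcome 2 analysis as adjusted for the three catchment-level restriction covariates, in the form used for the restriction. Name one of two routes to inference:

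- a cluster-level regression of log prevalence on arm and the three covariates, tested on t with 27 df, with a stated rule for catchments with no positives (the simulation added 0.5 to each count); or
- a permutation test of the adjusted arm effect over the set of accepted allocations. This follows the randomisation actually used, though it was not simulated here. The accepted set must be retained.

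Do not simply add the covariates to a maximum-likelihood mixed model with a z or t(27) reference, which rejected 6.6 to 8.3% of null trials. Keep the unadjusted model as a sensitivity analysis.

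The cost is a wording change and three of 30 degrees of freedom. All three covariates are known before randomisation, so no new data are needed. The cluster-level route reports a prevalence ratio, where the mixed model reports an odds ratio, and the text should say so.
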